## **POTENTIAL PROBLEM AREAS & ALTERNATIVE METHODS/APPROACHES**

**Pitfall #1:** The arrival of evidence-based antiviral therapies (e.g., remdesivir) may alter the clinical course of the disease(174), *however this has not yet been established and while some studies suggest remdesivir provides a modest benefit, interim analysis of the large WHO SOLIDARITY trial suggest no mortality benefit (175).*

**Alternative:** We will model clinical trajectories after initiation of anti-viral therapy by dichotomizing the study cohort into two groups: short versus long recovery time. By comparing these groups, we expect to identify an effective prediction algorithm from our baseline dataset for higher (shorter time to recovery) versus lower functional recovery potential (longer time to recovery). It will be important to analyze for corticosteroid treatment, which has become routine treatment for severe COVID-19(34), and was recognized as a potential contributor (e.g., steroid myopathy) to long-term sequelae in the SARS epidemic(176).

**Pitfall #2:** The implementation of effective vaccine strategies may alter the recruitment modeling for our study.

**Alternative:** Rapid vaccine implementation is a major initiative in the fight against COVID-19 and there are several parallel efforts(177-181). Thus, it is quite likely that an effective vaccine against COVID-19 will be implemented during the study period. While it is difficult to predict with precision when vaccination levels will provide effective herd immunity and thus lead to a significant reduction in cases, it is unlikely that this will happen in less than 1.5 years(178). It is also unlikely that a vaccine strategy will be so effective that it will prevent all disease or eliminate the disease entirely. The latter has happened with only a single human pathogen to date, and the worldwide effort to eliminate smallpox took well over two decades of sustained effort. It is currently not thought to be possible to effectively eradicate an infection that has an animal reservoir (like SARS-CoV-2). Our goal is to enroll 3.3 patients/week from 7 sites over 42 months (July 1, 2021 through December 31, 2024). Given the experience of the sites involved and the location of these sites in major metropolitan areas prone to high rates of COVID-19, we expect that the majority of subjects will be enrolled relatively quickly during the first half

of the enrollment period. Thus, we expect to be able to complete the study as designed even if there is rapid implementation of an effective vaccine strategy that affects our ability to recruit subjects in the latter years of the project.

**Pitfall #3:** Our predictive algorithm does not perform well on certain subgroups. **Alternative:** We think this is unlikely because the biological responses (or lack thereof) that lead to poor outcomes are likely to be similar among people with differences in demographic and underlying diseases (182, 183). However, in the validation process, we will look at important subgroups to see if there are issues with performance. While we have guarded against a sub-group imbalance by proposing a dual strategy, combining a civilian population in one of the country's largest metropolitan areas and a representative National Veteran's population, it is possible that our algorithm may not be as accurate in predicting outcome in subgroups (e.g., women versus men). If this is the case, we will train the algorithm on the specific subgroup only and determine whether we identify different parameters. Using this approach, we may also uncover clues pointing to underlying pathogenic mechanisms in SARS-CoV-2 infection.

**Pitfall #4:** Currently, there is not enough data available to develop a clinical phenotype scale for COVID-19. **Alternative:** We will have a comprehensive outcome list and will be able to explore a more detailed way of characterizing COVID-19 outcomes by the end of our study. In order to better define clinical phenotypes, we will correlate molecular and clinical data from our 500 patients to a tentative 10-point COVID-19 Functional Recovery Scale, modified from the WHO 8-point ordinal scale (**Figure 7**)(44, 174). Since the COVID-19 landscape is continually changing, we will modify this scale as necessary. The COVID-19 Functional Recovery Scale scores will be assessed by tele-medicine or in-person visits at baseline, discharge (secondary endpoint) and one-year (primary endpoint). An ordinal scale of continuous phenotypes may provide better power for outcome prediction than a scale that only detects presence or absence of adverse outcome.

**Pitfall #5:** SARS-CoV-2 genetic drift may affect outcomes. **Alternative:** As SARS-CoV-2 spread geographically and temporally, its genetic diversity increased (184, 185), and several genetic subgroups have already been defined. Certain mutations have been associated with higher mortality (186, 187), while others demonstrate improved binding to the respiratory tract (188, 189). It is currently not clear how viral evolution has affected the development or prevalence of sequelae and outcomes in general. To examine this crudely, we will monitor trends over the study period (i.e., early versus late). However, other time-specific effects could confound this analysis. The SUPERNOVA study is collecting respiratory samples for SARS-CoV-2 genome analysis. By integrating this information, we could look for differences based on genetic lineages.

**Pitfall #6:** Impact of influenza or other seasonal respiratory viruses on COVID-19. **Alternative:** While co-infection with SARS-CoV-2 and influenza virus have been described (190, 191), it remains unclear how influenza or other seasonal respiratory viruses will impact COVID-19. Additional studies are needed to establish whether viral co-infections in SARS-CoV-2 patients could potentially drive viral interference or otherwise influence disease outcomes (192, 193). It is possible that steps taken to mitigate spread of SARS-CoV-2, may significantly reduce influenza rates (194), as appears to have happened in Australia (195). However, if both viruses are prevalent, co-infection is certainly possible and may be common. All patients admitted to the enrolling sites with suspecting respiratory viral infection, will be tested for both SARS-CoV-2 and influenza. We will include co-infected patients in our analyses. If we enroll enough patients with infection with SARS-CoV-2 and influenza or another seasonal respiratory virus, we will further analyze this subset.

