**Patient Population.** We plan to complete 1-year follow-up in 500 patients from a large US-metropolitan area (LA-County) (n=250) and four national metropolitan VA centers (n=250). To account for a dropout rate of ~17%, we will recruit a total of 600 patients. LA-County is one of the largest metropolitan areas in the US. As per October 30, 2020, there were 290,278 laboratory confirmed cases, 24,670 hospitalized patients and 6,999 deaths(104). Since the first reported case of COVID-19 in the US, the four VA sites in Atlanta, Bronx, Houston and Los Angeles, have admitted 847 Veterans. While these sites vary in their COVID-19 experiences, combined they appear to be representative of the National VA population (**Table 1, re-submission Introduction**). These four sites belong to the SUPERNOVA consortium, which is a CDC-funded study ongoing for over 5 years that performs active surveillance for acute gastroenteritis and respiratory infection, including COVID-19 (28). The local site investigators are infectious disease physicians and have study staff trained in enrolling and following patients with infections. Study staff are well versed in identifying patients admitted with COVID-19, using a combination of admission log screening and TheraDoc (clinical surveillance software that integrates with the electronic medical record). Coordinators at the sites are experienced with abstraction of clinical data into REDCap and obtaining, processing, storing and shipping biological specimens. **Inclusion criteria.** Adult COVID-19 patients admitted to the hospital with any symptoms, including pneumonia, ARDS, sepsis, and septic shock(44) will be approached for consent (UCLA Informed Consent Form 20-000763, PI [name]). Since a majority of COVID-19-related deaths and hospitalizations are in male patients, we expect to enroll more men than women (9). **Exclusion criteria.** 1) Lack of consent by either patient or legally authorized representative, 2) <18 years old, 3) COVID-19 re-infection.

**Endpoint Definition.** Clinical composite endpoints will include new onset or worsening frailty, single organ dysfunction, multi-organ dysfunction, and death within one year (primary endpoint) and at time of discharge (secondary endpoint).

**Figure 1.** COVID-19 clinical decision making, study population and primary endpoint [modified after(96)].

**Figure 2.** Study design.

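### The Pitfall #1 contingency analysis cuts recovery time into short versus long, which discards information and gives patients who die before recovering no stated group

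*Protocol*

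**What the plan says.** The split is in the Protocol, Potential Problem Areas & Alternative Methods/Approaches, Pitfall #1. The pitfall is that "The arrival of evidence-based antiviral therapies (e.g., remdesivir) may alter the clinical course of the disease". The alternative begins "We will model clinical trajectories after initiation of anti-viral therapy", to be done by "dichotomizing the study cohort into two groups: short versus long recovery time". The two groups are labelled "higher (shorter time to recovery) versus lower functional recovery potential (longer time to recovery", and comparing them is expected to give a prediction algorithm from baseline data. The same paragraph says corticosteroid treatment should be analysed. It gives no cut-point, no definition of recovery and no rule for patients who die or do not recover.

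Four other places bear on this:

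- **Pitfall #4, same section.** Data from the 500 patients are to be related to a tentative 10-point Functional Recovery Scale, scored at baseline, discharge and one year. The stated reason is that an ordinal scale "may provide better power for outcome prediction than a scale that only detects presence or absence of adverse outcome".
- **Summary, Figure 7.** Death is level 1 of that scale, the most severe.
- **Research Plan, Endpoint Definition.** The composite endpoint covers "new onset or worsening frailty, single organ dysfunction, multi-organ dysfunction, and death within one year (primary endpoint", so deaths are expected.
- **Research Plan, Data Collection.** Clinical data are collected at baseline, discharge and one year. No recovery date is listed.

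**The concern.** A two-level version of a time outcome treats all patients on one side of the cut as alike. It weakens any association with a marker, and the result depends on where the cut falls. The protocol gives no reason for accepting this, and under Pitfall #4 it makes the case for a graded outcome.

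Both groups are defined by time to recovery, yet the split is applied to the whole study cohort. A patient who dies unrecovered has no such time. Leaving these patients out, counting them as long, or classing them by time of death are three different analyses and can give different answers for the same marker.

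At stake is the sensitivity and the interpretation of one fallback analysis. The main analysis is not in question.

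**Working it through.** **1. The plan's own figure.** The protocol gives no sample size, power, cut or effect size for this analysis, so there is nothing to reproduce. The nearest figures are "We plan to complete 1-year follow-up in 500 patients" and "To account for a dropout rate of ~17%, we will recruit a total of 600 patients". Here 500/(1 − 0.17) = 602.4, or 603 rounded up, against 600 stated, and 1 − 500/600 = 16.7%. These agree to rounding and do not depend on the split.

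**2. Loss under a normal model.** Assume log recovery time is roughly normal and fully observed. For a cut leaving a share p on one side, the information kept is φ(z_p)² / [p(1 − p)]. At the median this is 0.3989²/0.25 = 2/π = 0.637.

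| Cut | Kept | Lost | 500 patients count as |
|---|---|---|---|
| 50/50 | 0.637 | 36% | 318 |
| 40/60 | 0.622 | 38% | 311 |
| 30/70 | 0.576 | 42% | 288 |
| 20/80 | 0.490 | 51% | 245 |
| 10/90 | 0.342 | 66% | 171 |

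**3. Power.** For 80% power at two-sided 5% the standardised effect is 1.96 + 0.84 = 2.80. A median split multiplies it by √0.637 = 0.798, giving 2.235. Power is then Φ(2.235 − 1.96) = Φ(0.275), about 61%.

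**4. Against other undivided analyses.**
- Rank or proportional-odds: the share kept is 3p(1 − p). At the median this is 0.75 (25% lost); at 20/80 it is 0.48 (52% lost).
- Uncensored proportional hazards: with F the share recovered by the cut and S = 1 − F, the share kept is (ln S)²·S/F. At F = 0.5 this is 0.480 (52% lost). At F = 0.8, close to the best cut, it is 0.648 (35% lost).

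**5. Deaths.** The protocol gives no separate one-year death rate. Assumed rates of 5%, 10% and 20% leave 25, 50 and 100 of 500 patients with no recovery time if all those deaths precede recovery.

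To see whether the handling rule matters, a standard normal marker x was simulated in 400,000 patients. All values are assumed:
- log-odds of death = −1.9 + 1.0x, which gives 17% deaths;
- log recovery time = 2.3 + 0.35x + 0.7 × normal noise;
- log time of death = 2.0 + 0.6 × normal noise;
- cut at the median recovery time of survivors.

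The marker's AUC was 0.70 with deaths left out, 0.73 with deaths counted as long, and 0.64 with deaths classed by time of death. These figures illustrate that the rule matters; they are not estimates for this study.

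**6. The two pitfalls side by side.** Pitfall #1 reduces a graded quantity to two levels. Pitfall #4 prefers grades to two levels for reasons of power, and its scale has a place for death. Pitfall #1 does not refer to that scale.

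**The case against.** - **Scope.** This is an alternative under a listed pitfall. The primary analysis uses the one-year composite, which counts death as an event, with LASSO logistic models compared by AUC. Recovery time does not enter it. A reader might infer that the fallback could become a main result. The protocol does not say it would replace the primary endpoint, and the same paragraph doubts that antivirals have yet been shown to change the course of disease. This objection stands.
- **Deaths.** A reader might infer that deaths are excluded and the markers therefore biased towards survivors, or that no valid group exists for them. Neither is written. Deaths could be placed in the group with lower recovery potential, in line with Figure 7. The rule, the cut and the definition of recovery may also be in a statistical analysis plan that is not at hand. What stands is narrower: the groups as worded give deaths no stated place.
- **Size.** A reader might take a loss of about a third as a property of the plan. It follows from an assumed median cut and an assumed distribution. The power figure also concerns detecting one marker's association, whereas the paragraph aims at a prediction algorithm. The range has to be shown.
- **Pitfall #4.** It concerns a severity scale, not recovery time, and says only that power may improve. It is not a formal contradiction, and it means an ordinal analysis is already planned alongside. The reasoning carries over all the same, and the dichotomy is a stated method, not a detail left open.

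**Conclusion.** The point holds as a minor improvement to a contingency analysis. The dichotomy is fixed in the protocol, loses information at any cut, and gives patients who die before recovering no stated group. Under the stated assumptions the loss is about 36% for a median split of a roughly normal log time (80% power becomes about 61%), about 25% against a rank or proportional-odds analysis at the median, and about 51% for a 20/80 cut under the normal model. All three rest on fully observed recovery times and on cuts the protocol does not give. The documents do not support saying that deaths are dropped, or that any stated result of the study is invalid. The primary endpoint, the 500/600 sample size and the Aim 2 AUC comparisons are unaffected.

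**What to change.** In the Pitfall #1 alternative, replace the short/long split with an analysis of the undivided outcome. Either of these would do:

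1. The Functional Recovery Scale already planned at discharge and one year, analysed as ordinal with death as the worst level.
2. Time to recovery with death as a competing event, using cumulative incidence with cause-specific or Fine-Gray models. Recovery is defined from dates actually collected, such as discharge.

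In either case include antiviral and corticosteroid exposure in the model. For option 2, state the time origin, because time from the start of antiviral therapy is undefined for patients who receive none. Keep the short and long groups for description only.

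**Cost.** Option 1 needs no new data, since the scores are already planned. The tentative scale must be fixed before analysis. It measures status at set times, not speed of recovery, and regains less of the loss if few levels are occupied. Option 2 needs no dates that the short/long split would not also need, but recovery must first be defined from the available assessments. With clinical data collected only at baseline, discharge and one year, recovery after discharge is known only within an interval. It should not be assumed that every date needed is already in the record.

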
**Sample Size Requirements and Power Calculations.** Current available literature suggests that at least 20% of the symptomatic COVID-19 infected population may develop frailty, organ dysfunction or death within one year(46, 47, 52, 56, 57, 61, 62, 113-116). Based on these assumptions, we will perform power calculations on the following numbers (250 civilians, 250 Veterans) (**Figure 2**): Aim 1.1 single-omic identification (n=100, 80 endpoint negative/20 endpoint positive) and confirmation (n=200, 160 endpoint negative/40 endpoint positive) of candidate genomic, transcriptomic, proteomic and clinical parameters that correlate with outcomes; Aim 1.2 multi-omics correlation analysis (n=300 from Aim 1.1, 240 endpoint negative/60 endpoint positive); Aim 1.3 WGCNA and pathway analysis (n=300 from Aim 1.1); Aim 2.1 training/testing of the predictive algorithm (n=300 from Aim 1.1); Aim 2.2 independent validation of predictive algorithm (independent n=200). Samples will be processed in 5 batches, approximately 120 samples per year within 5 years. Statistical analysis will begin after one-year outcomes of the first 100 patients have been collected. Patients will be stratified by outcomes, Veteran/civilian status, age, gender, ethnicity, comorbidities, frailty and other parameters that appear to be significant such as alcoholism.

**Timeline.** The timeline of the entire project is summarized in **Table 3**. We anticipate that: 1) recruitment of 600 COVID-19 patients will be begin 3 months after funding start, be completed within 42 months, 2) the 12-month follow-up period will be completed by month 57, and 3) the analysis will be completed by month 60.

Immune Cell Subsets	
Cell Population	Phenotype
T cells	CD3+CD4+ or CD3+CD8+
Naive	CCR7+CD45RA+
Effector Memory	CCR7-CD45RA-
Central Memory	CCR7+CD45RA-
TEMRA	CCR7-CD45RA+
Activated Effector	CD25++CD127hi
Regulatory	CD4+CD25++CD127lo
Antigen-experienced	KLRG1+
Limited capacity memory	CD38+
Chronically activated	CD57+
Activated suppressive	PD1+
Natural Killer Cells	CD3-CD56+
Cytotoxic	CD56dimCD16+
Cytokine producing	CD56brightCD16+
B Cells	CD19+
Transitional	CD38++CD24+
Mature Naive	CD27-IgD+
Memory	CD27+
Non-Switched memory	CD27+IgD-
Switched Memory	CD27-IgD+
Plasmablasts	CD27+CD38++
Regulatory	CD5+CD24+

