## **AIM 2: TRAIN AND VALIDATE ALGORITHM FOR OUTCOME PREDICTION**

**Hypothesis and Objectives.** We hypothesize that our algorithm will predict COVID-19 short- and long-term outcomes more accurately than clinical parameters alone. Our objectives are to train the algorithm in a mixed US-high risk COVID-19 population (Aim 2.1) and validate the predictive algorithm on an independent mixed US-high risk COVID-19 population (Aim 2.2).

**Aim 2.1: Train algorithm for outcome prediction. Objective.** Our objective is to train and test our algorithm in a mixed US COVID-19 population, which will improve prediction of adverse short- and long-term outcomes(92, 173). **Bioinformatics. Parameter Selection.** Model development will largely follow the modeling reported in the preliminary data section and will be constructed using significant entities identified in the marker screening phase (Aim 1). Since VA and civilian patients may have different co-morbidity and risk profiles, these models will also include a term for whether the patient is from the VA or civilian setting. This term, if significant, will allow flexibility in our models to make different predictions based upon known characteristic differences between VA and civilian patient populations. **Power calculations.** The first 300 samples (240 endpoint negative and 60 endpoint positive)

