will be used for model building (**Figure 2**). The overall sample size will support the following: 1) This sample size will be sufficient to include approximately 10 clinical features based on conventional rules of thumb suggesting that we should have 10-15 subjects in the less frequent outcome category per variable in a logistic regression model; 2) This will allow us to estimate the AUC for the model with a precision of approximately 0.032 (based on the 95% confidence interval for the AUC and an overall AUC of at least 0.8); 3) Provide 80% power for detecting delta AUCs between pairs of models (see below) of 0.1 assuming that the models will have a correlation of 0.5 and AUCs of ~0.8. **Logistic regression modeling. Logistic regression modeling.** We will assess the algorithm by constructing three separate logistic regression models, one using clinical factors alone as our baseline model, one using clinical factors plus the significant omics markers from the screening phase (genomics, transcriptomics, and proteomics parameters), and one using clinical factors plus a simplified list of significant omics features (e.g. bedside, rapid test, easy to obtain). Each of the three models will have variable selection and coefficients estimated by the LASSO method and validation results and comparisons between the three models performance (AUC) will be validated in Aim 2.2. **Model building optimization by cross-validation.** Ten-fold cross-validation will be used to estimate model performance in terms of AUC. The AUCs will be compared between models with DeLong's test for paired AUCs. **Interpretation of Results.** We expect to derive a multi-omics algorithm that will predict outcomes of COVID-19 patients more accurately than clinical data alone.

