**Aim 2.2: Independently validate predictive algorithm for outcome prediction. Objective.** Our objective is to validate the algorithm in an independent randomly selected mixed US COVID-19 population who were not used for algorithm development(173). **Bioinformatics.** We will validate the performance of the prototype test algorithm to predict the composite endpoints in an independent cohort of 200 patients (**Figure 2**). Rigorous testing of the analytical performance of the test will identify and quantify the technical variations of the test performed on the patient samples and will be done in a blinded fashion, without knowledge of the clinical status or treatment outcomes of the patients whose data was obtained. For model testing, the sample size of 200 (160 endpoint negative and 40 endpoint positive) will provide precision of +/- 0.066 for the testing AUC as well as an 80% power to detect differences in AUCs between models of 0.12, when comparing models based on clinical features alone and models combining clinical and molecular features. Finally, with this sample size we will be able to estimate the precision of the sensitivity and specificity (based on the width of the 95% confidence intervals) between 0.0545 to 0.11 depending on the observed values of those performance characteristics. *We plan to make the raw data and the algorithm publically available as a web-based free tool for further scientific development by the international scientific community.* **Interpretation of Results.** We expect that the algorithm will confirm the desired clinical test performance, i.e. increase accuracy of one-year primary endpoint (new onset or worsening frailty, organ dysfunction or death) prediction of at least AUC 0.12.

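### If a subgroup looks poor in validation, Pitfall #3 retrains on that subgroup alone: for women on roughly 13-19 training events, with no clean data left to test the result

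*Protocol*

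**What the plan says.** The contingency stands under Pitfall #3 in the protocol's section on potential problem areas. The protocol thinks poor subgroup performance unlikely, because it expects similar biology across patient groups, but it commits to a check: "in the validation process, we will look at important subgroups to see if there are issues with performance". It allows that "our algorithm may not be as accurate in predicting outcome in subgroups (e.g., women versus men", and then fixes the response: "we will train the algorithm on the specific subgroup only and determine whether we identify different parameters". It adds that this may give clues to disease mechanisms. It sets no threshold for an issue with performance, does not say which samples the refit would use, and attaches no exploratory label.

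Four statements elsewhere bear on this:

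- Event rate (Research Plan, sample size paragraph): "at least 20% of the symptomatic COVID-19 infected population may develop frailty, organ dysfunction or death within one year".
- Model building (Aim 2.1): "The first 300 samples (240 endpoint negative and 60 endpoint positive", with the rule that "we should have 10-15 subjects in the less frequent outcome category per variable in a logistic regression model".
- Validation (Aim 2.2): "the sample size of 200 (160 endpoint negative and 40 endpoint positive) will provide precision of +/- 0.066 for the testing AUC". The sample size paragraph lists this cohort as "Aim 2.2 independent validation of predictive algorithm (independent n=200".
- Differences between VA and civilian patients (Aim 2.1) are handled by a setting term in a pooled model, not by separate models.

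**The concern.** Three weaknesses compound. The signal that starts the retraining comes from a small part of a 200-patient set. The response discards every patient outside the flagged subgroup, so variable selection among clinical and omics features would run on very few events. No further cohort exists in which to test the result. Features that differ from those of the main model would then be hard to tell from sampling noise, yet the protocol proposes to read them as possible mechanistic clues. The response also sits badly with the protocol's own premise of similar biology, which argues for pooling.

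**Working it through.** **1. The plan's own figures.** 300 × 0.20 = 60 and 200 × 0.20 = 40 events, as stated. The Hanley-McNeil formula with 40 events and 160 non-events gives a 95% half-width of 0.0657 at an AUC of 0.90, which matches the stated 0.066. At 0.80, the AUC assumed in Aim 2.1, it gives 0.087. The formula is therefore a fair tool here, and 0.80 is used below.

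**2. Events in women.** Inputs from the protocol: a 20% event rate, 250 VA and 250 civilian completers, and about 87% men among Veterans (Significance, Epidemiology), hence 13% women as a proxy for the VA patients. Assumptions: each analysis set is half VA, the event rate is the same in both sexes, and the share of women among civilians, *f*, is 30-50%. The protocol says only that men will outnumber women.

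Women = N/2 × 0.13 + N/2 × *f*; events = 0.20 × women.

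| *f* | Women (events), 300 training | Women (events), 200 validation | Women (events), all 500 |
|---|---|---|---|
| 30% | 64.5 (12.9) | 43.0 (8.6) | 107.5 (21.5) |
| 40% | 79.5 (15.9) | 53.0 (10.6) | 132.5 (26.5) |
| 50% | 94.5 (18.9) | 63.0 (12.6) | 157.5 (31.5) |

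Variables supported at 10-15 events each:

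- Training set: from 12.9/15 = 0.9 to 18.9/10 = 1.9.
- All 500: from 21.5/15 = 1.4 to 31.5/10 = 3.2.
- Pooled training set: 60/15 = 4 to 60/10 = 6.

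Other subgroups are larger. Veterans or civilians have 150 × 0.20 = 30 training events each, and men have 60 − 18.9 = 41.1 to 60 − 12.9 = 47.1.

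**3. Precision of the validation check.** SE² = [A(1−A) + (n₁−1)(P−A²) + (n₀−1)(R−A²)]/(n₁n₀), with P = A/(2−A) and R = 2A²/(1+A). At A = 0.80, P = 0.6667 and R = 0.7111.

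For *f* = 40% (10.6 events, 42.4 non-events): SE² = (0.160 + 9.6 × 0.0267 + 41.4 × 0.0711)/449.4 = 0.00748, so SE = 0.0865 and the half-width is 1.96 × 0.0865 = 0.169. The same formula gives 0.189 at *f* = 30% and 0.155 at 50%.

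To illustrate, suppose the true AUC is 0.80 in both sexes. The SE of the women-minus-men difference is about 0.101 (*f* = 40%) or 0.096 (50%). The women's AUC then falls at least 0.05 below the men's in about 30% of studies, and at least 0.10 below in about 15%. These two cut-offs are illustrations; the protocol has none.

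**4. Data left for testing.** 300 + 200 = 500, which is every planned completer. If the refit uses the 300, the 200 remain outside the fit, but they have already served to pick the subgroup and hold only about 9-13 events in women. If the refit uses all 500, nothing remains. Neither route leaves a clean test.

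**5. Does subgroup-only training predict worse?** A LASSO simulation gives a guide. Assumed settings: 300 patients, 87 of them women, 30 candidate features of which 8 are predictive, 40 replicates. Mean AUC in new women:

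| Share of predictors that differ by sex | Women only | Pooled | Pooled with penalised interactions |
|---|---|---|---|
| 0% | 0.67 | 0.81 | 0.81 |
| 25% | 0.68 | 0.76 | 0.77 |
| 50% | 0.67 | 0.70 | 0.73 |
| 75% | 0.67 | 0.64 | 0.68 |
| 100% | 0.68 | 0.57 | 0.65 |

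A separate run with 80 women and 80 replicates gave the same pattern for plain pooling against women only: 0.79 v 0.65, 0.75 v 0.67, 0.68 v 0.65 and 0.63 v 0.66 at 0, 25, 50 and 75% difference.

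**The case against.** The strongest reply is that this is a contingency for an event the protocol thinks unlikely, and that its stated purpose is to see whether different parameters emerge. A reader might infer that the refitted model would replace the main algorithm or be presented as validated. The protocol says neither, and the Aim 2.2 validation of the main algorithm is untouched. That stands, and it limits the point to how the contingency is specified.

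Three further stronger readings also fail:

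- **That the plan both refits on under 20 events and uses up the validation set.** These belong to different scenarios. The low count arises if only the 300 are used; the 200 are consumed only if all 500 are used, which gives about 22-31 events in women. The low count is also not general: Veterans or civilians would have about 30 training events. And 20% is a floor, so counts would rise with the rate; at an assumed 30%, women would have 64.5 × 0.30 = 19 to 94.5 × 0.30 = 28 training events.
- **That a known false-alarm rate applies.** No threshold is stated, so the 30% and 15% figures describe assumed cut-offs. What the documents support is the width of the interval.
- **That the refit must perform worse.** Against plain pooling, women-only training did better when 75% of predictors differed, which is the kind of failure the contingency is meant for. Against pooling with interactions it led only when no predictor was shared.

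It is also fair that the events-per-variable rule was stated for sizing clinical features while the models select by LASSO, and that the main model already sits tight against the rule. The rule is used here only as the protocol's own yardstick of how little information a subgroup holds.

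**Conclusion.** The point holds in a limited form. The protocol fixes a response to apparent subgroup failure that, for its own example of women, rests on about 13-19 events in the training set or about 22-31 in all 500. The check that prompts it has an AUC half-width of about 0.16-0.19, and no clean data remain for testing. Subgroup-only training is likely, not certain, to predict worse than a pooled model with subgroup terms, and different parameters found this way may be noise. The counts depend on the assumed sex mix, an even VA/civilian split in each set and a 20% event rate in both sexes. The comparison of methods depends on assumed feature numbers and effects. The primary validation is not affected; a change is advisable because a better method is available at little cost.

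**What to change.** In Pitfall #3, replace training on the specific subgroup only with the following:

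- Keep all patients in the model.
- Test the subgroup-by-score interaction and report it with its confidence interval, since the test will have little power.
- If needed, recalibrate, or add penalised subgroup interaction terms to the pooled model. Recalibration corrects risk levels but not the ranking within a subgroup; poor discrimination needs the interaction terms. This extends the approach of Aim 2.1, which already puts a VA/civilian term in a pooled model.
- Report cross-validated performance, and state which samples were used.
- Label any subgroup-specific algorithm or parameters exploratory until tested in new data.

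The cost is a change of wording and a little more code. The downside is that no stand-alone subgroup algorithm could be claimed from this study.
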